8 TRIAL TREATMENTS

8.1 Name and description of treatment

This trial will use the atypical antipsychotic olanzapine as the treatment. Olanzapine is a dopamine D1, D2, D4, 5-HT2, histamine- 1-, and muscarinic-receptor antagonist. In this study, olanzapine will be used as tablet or as a dispersible tablet, of 2.5, 5, 7.5 or 10 mg. Olanzapine is UK-licensed and commercially

Page 39 of 60

available on the UK market. Any brand/manufacturer of Olanzapine with a marketing authorisation in the UK can be used.

8.2 Regulatory status of the drug

Olanzapine has a marketing authorisation in the UK. It will be used in its marketed presentation and packaging. For this trial, the product will not be further processed, e.g., by repackaging or by trial labelling.

Olanzapine is indicated and approved for:

- Treatment of schizophrenia
- Acute treatment of manic or mixed episodes associated with bipolar I disorder
- Maintenance treatment of bipolar disorder

These indications apply to adult patients.

8.3 Product Characteristics

Olanzapine is an atypical antipsychotic used in and approved for the treatment of schizophrenia and bipolar disorder. Olanzapine is currently widely used for the treatment of AN even though it is not approved in this indication. This feasibility study will use it in this indication in order to inform the feasibility of a future definitive RCT. Apart from its use in AN which is not a current indication for olanzapine all BNF standards apply for this trial.

8.4 Drug storage and supply

Drug storage and supply will follow the policies of the involved NHS Mental Health Trusts and the pharmacies serving the patients. There are no specific requirements for this feasibility study apart from the guidelines and legislation that apply for the use of olanzapine in the UK.

Olanzapine will be sourced locally by the research site pharmacy at market price.

For this trial, there are no special arrangements for prescription, storage and dispensing of olanzapine.

8.5 Preparation and labelling

• No labelling of Olanzapine will be required since it is a feasibility study, and the study drug will be used from commercial stock and according to its SmPC.

8.6 Dosage schedules

In this feasibility study, we will initiate olanzapine treatment at 1.25 mg/d or 2.5 mg/d in adolescent patients and continue this dose or increase the dose slowly to up to 10 mg/d. *In adults, the start dose will be 2.5 mg/d*. Patients can maintain this dose if it is deemed sufficient. This will be a clinical decision. This dosage is within the British National Formulary (BNF) limits.

8.7 Dosage modifications

The study will follow a slow up-titration schedule (1.25 or 2.5 mg/d increments each week for adolescents and 2.5 mg/d for adults up to a maximum of 10 mg/d for both adolescents and adults). This is the dose range we would also apply in an RCT. Olanzapine does not come as a 1.25mg/d tablet so clinicians will be instructed the halve the 2.5mg/d tablet in initial dosages.

The same down-titration increments apply after 12 months to improve patient safety. However, it will be a clinical decision outside our study whether patients continue or stop olanzapine treatment.

Page 40 of 60

8.8 Known drug reactions and interaction with other therapies

The current recommended therapeutic elements to treat AN are psychotherapy, diet counselling and physical monitoring. Thus, there is no specific combination or concomitant medication to be expected in the patient group of this study.

The following combinations are, in principle, known to lead to potential drug interactions:

- Diazepam: May potentiate orthostatic hypotension.
- Alcohol: May potentiate orthostatic hypotension. Alcohol dependence is an exclusion criterion of this trial. Patients will be advised not to drink alcohol during the trial.
- Carbamazepine: Increased clearance of olanzapine.
- Fluvoxamine: May increase olanzapine levels.
- CNS Acting Drugs: Caution should be used when taken in combination with other centrally acting drugs and alcohol.
- Antihypertensive Agents: Enhanced antihypertensive effect.
- Levodopa and Dopamine Agonists: May antagonize levodopa/dopamine agonists.
- Lorazepam (IM): Increased somnolence with IM olanzapine.
- Other Concomitant Drug Therapy: When using olanzapine in combination with lithium or valproate, we will refer to the Drug Interactions sections of the package insert for those products.

Fluoxetine is available in a fixed combination with olanzapine (Symbyax®). This combination is indicated for the treatment of depressive episodes associated with bipolar I disorder or treatment resistant depression. In adolescents, the daily dose should be below 12 mg. However, in this trial 10 mg olanzapine is the maximum daily dose.

8.9 Concomitant medication

Caution is advised for the drugs listed in the previous section as concomitant medication. However, there is no contraindication for the monotherapy with olanzapine. Additionally, blood concentration of olanzapine will be monitored throughout the study. Contraindications according to the BNF apply to elderly patients who will not be included in this trial and to patients who receive olanzapine as intramuscular application which is not envisaged in this trial either.

8.10 Contraception Guidelines

Contraception needs to be used and the duration for use.

A woman is considered of childbearing potential (WOCBP), i.e., fertile, following menarche and until becoming post-menopausal, unless permanently sterile. Permanent sterilisation methods include hysterectomy, bilateral salpingectomy, and bilateral oophorectomy. A postmenopausal state is defined as no menses for 12 months without an alternative medical cause. A high follicle stimulating hormone (FSH) level in the postmenopausal range may be used to confirm a post-menopausal state in women not using hormonal contraception or hormonal replacement therapy. However, in the absence of 12 months of amenorrhea, more than one FSH measurement is required. A man is considered fertile after puberty unless permanently sterile by bilateral orchidectomy.

For females of childbearing potential who may participate in the study, the following methods of contraception, if used properly and used for the duration of the study, are considered sufficient:

- Oral, patch or injection combined or progestestogen only contraceptives. Hormonal contraception must be associated with inhibition of ovulation
- Intrauterine device
- Surgical sterilization

- Vasectomized partner provided that partner is the sole sexual partner of the WOCBP trial participant and that the vasectomised partner has received medical assessment of the surgical success.
- Sexual abstinence. Sexual abstinence is considered a highly effective method only if defined as refraining from heterosexual intercourse during the entire period of risk associated with the study treatments. The reliability of sexual abstinence needs to be evaluated in relation to the duration of the clinical trial and the preferred and usual lifestyle of the subject.

Periodic abstinence, i.e., calendar, symptothermal, or post-ovulation methods are not an acceptable form of contraception for this study.

Male participants will be required to use condoms. Male participants not willing to follow the contraception advice will be excluded.

The duration of contraception required is defined as until the end of the study.

8.11 Assessment of compliance with treatment

Compliance will be assessed by

- Measurement of the olanzapine plasma level 8 weeks after baseline
- Pill count, self-reported by the patient at 8 weeks, 16 weeks, 6 months, and 12 months after baseline.

Noncompliance to the protocol trial procedures will be documented by the investigator. Noncompliance will not lead to withdrawal from the trial. This is a feasibility study which will find out the rate of compliance or noncompliance as well as the rate of participation in assessments and assessment completion.

Compliance and non-compliance are part of the qualitative research aspect of this feasibility study.

9 PHARMACOVIGILANCE

9.1 Definitions

The Medicines for Human Use (Clinical Trials) Regulations 2004 and Amended Regulations 2006 gives the following definitions:

- Adverse Event (AE): Any untoward medical occurrence in a participant to whom a medicinal product has been administered, including occurrences which are not necessarily caused by or related to that product.
- Adverse Reaction (AR): Any untoward and unintended response in a participant to an investigational medicinal product which is related to any dose administered to that participant.
- **Unexpected Adverse Reaction (UAR)**: An adverse reaction the nature and severity of which is not consistent with the information about the medicinal product in question set out in:

The summary of product characteristics (SmPC) for that product (for products with a marketing authorisation)

- Serious adverse Event (SAE), Serious Adverse Reaction (SAR) or Suspected Unexpected Serious Adverse Reaction (SUSAR): Any adverse event, adverse reaction, or unexpected adverse reaction, respectively, that:
 - results in death;
 - is life-threatening;

- required hospitalisation or prolongation of existing hospitalisation;
- results in persistent or significant disability or incapacity;
- consists of a congenital anomaly or birth defect.
- **Important Medical Events (IME) & Pregnancy:** Events that may not be immediately lifethreatening or result in death or hospitalisation but may jeopardise the participant or may require intervention to prevent one of the other outcomes listed in the definition above should also be considered serious. Although not a serious adverse event, any unplanned pregnancy will also be reported. In case of a pregnancy, study medication will stop. The pregnant study participant will be followed up until 12 months after baseline.

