4 TRIAL DESIGN

The design of this feasibility study is open treatment of 55 patients with olanzapine for 12 months. Participants will be examined at baseline, and at 8 weeks, 16 weeks, 6 months and 12 months after start of treatment. This is a one-arm open treatment design, there is no placebo and no comparator.

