7.1.2 Screening

The aim of the screening process is to ascertain whether inclusion and exclusion criteria are met. In accordance with the inclusion and exclusion criteria outlined in section 6.1. and 6.2., the clinical research team will update the eCRF with the following information about the potential participant after informed consent is obtained:

- Age
- Gender
- Diagnosis of AN
- Level of nonresponse to TAU (at least one month of treatment; weight gain <2 kg within at least one month of TAU; outpatients should have attended ≥4 therapeutic sessions.
- Potential serious self-harm, suicidality, psychotic disorder
- Serious medical comorbidities which are contraindications for olanzapine
- Current alcohol or illicit drug use disorder
- Use of major tranquilliser or opioids
- QTc time
- Liver function tests or white cell count
- Use of other medication at stable dose for <4 weeks
- Use of medication potentially interacting with olanzapine
- Pregnancy test, willingness to take further pregnancy tests after 8 weeks, 16 weeks, 6 months, and 12 months and to take contraceptive measures as specified in section 8.10. on trial restrictions (females of childbearing potential only)
- Breast feeding
- Capacity of the adult participant or the adolescent participant and their legal representatives to agree to the study

For definition of serious self-harm and serious medical comorbidities see section 6.1. and 6.2.

To obtain this information and thus determine inclusion and exclusion criteria, a full psychiatric and medical history taking, physical examination and assessment will take place. See section 6.1. and 6.2. To obtain this information is included in the standard care for a patient with AN if pharmacological treatment is considered.

Page 31 of 60

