9.2 Recording and reporting of SAEs, SARs AND SUSARs

Reporting Responsibilities

All SAEs will be reported immediately to the Chief Investigator and to the Sponsor (excepting those specified in this protocol as not requiring reporting)

- All SAEs will be reported to the main REC where in the opinion of Chief Investigator (CI) the event was:
 - related that is, it resulted from administration of any of the research procedures, and
 - unexpected that is, the type of event is not listed in the protocol as an expected occurrence, within 15 days of the CI becoming aware of the event.

Death as a result of disease progression and other events that are primary or secondary outcome measures are not considered to be SAEs and should be reported in the normal way, on the appropriate CRF.

The active monitoring period for (S)AEs will end 13 months after baseline which is after down-titration of study medication. Following the active monitoring period, the CI will report any related or unexpected SAEs that he becomes aware of. Where a participant withdraws consent for further processing of data, this does not preclude the reporting of SAEs. The participant information sheet will include a section explaining this to the participant.

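### Pregnancy follow-up in section 9.1 stops at 12 months after baseline whatever the stage of pregnancy, so many birth outcomes would not be actively collected

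*Protocol*

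**What the plan says.** Section 4 sets the exposure period: "The design of this feasibility study is open treatment of 55 patients with olanzapine for 12 months". Pregnancy is an exclusion criterion (6.2), and at screening females of childbearing potential must show "willingness to take further pregnancy tests after 8 weeks, 16 weeks, 6 months, and 12 months".

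Section 9.1 lists as serious any event that "consists of a congenital anomaly or birth defect". On pregnancy it says "Although not a serious adverse event, any unplanned pregnancy will also be reported", then "In case of a pregnancy, study medication will stop", and then "The pregnant study participant will be followed up until 12 months after baseline".

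Section 9.2 adds: "The active monitoring period for (S)AEs will end 13 months after baseline which is after down-titration of study medication". After that, the chief investigator reports related or unexpected SAEs that come to his attention. Section 9.7 puts no time limit on reporting SUSARs to the ethics committee. Section 7.8 plans no assessments after month 12.

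Section 7.13.2 says participants will be told that a pregnancy means withdrawal from the study. No section asks for delivery, pregnancy outcome or the state of the newborn to be recorded.

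**The concern.** The end of pregnancy follow-up is fixed by the participant's entry date. Because pregnancy is excluded at screening, every on-study conception falls after entry, and a term birth falls some nine months or more into the study. The later the conception, the more of the pregnancy lies outside follow-up. The month-6 and month-12 tests mainly find pregnancies whose term outcome lies beyond the planned limit.

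At stake is the completeness of the safety record in a study that gives a drug off-label to participants aged 12 to 24. Followed exactly, the rule records that a pregnancy happened but often closes the file before its outcome. The quality of adverse event reporting is also one of the secondary feasibility aims in 3.2, so the reporting procedure matters even if cases are rare.

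**Working it through.** The protocol states no figure on this point, so there is nothing to reproduce. The check is date arithmetic.

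**Inputs from the protocol**
- Treatment lasts 12 months (section 4).
- Pregnancy follow-up ends at month 12 (9.1); active (S)AE monitoring ends at month 13 (9.2).
- Pregnancy tests are at 8 weeks, 16 weeks, 6 months and 12 months (7.1.2).
- The share taking olanzapine for at least 16 weeks is planned at 70%, with 50% as the extreme case (10.1).

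**Assumptions not in the protocol**
- Conception to term takes 38 weeks (range 34-40).
- Conceptions are spread evenly over time on drug.
- In the base case every participant stays on drug and every pregnancy goes to term.
- One month is 365.25/12 = 30.44 days.

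**Base case.** Time to term is g = 38 × 7 / 30.44 = 8.74 months. For a limit L, the latest conception that reaches term in time is L − g, and the share ending later is 1 − (L − g)/12.
- L = 12: 12 − 8.74 = 3.26 months (14.2 weeks); 1 − 3.26/12 = 72.8%.
- L = 13: 13 − 8.74 = 4.26 months (18.5 weeks); 1 − 4.26/12 = 64.5%.

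**Discontinuation.** Suppose time on drug is exponential with a fraction p still on drug at 16 weeks (3.68 months). Then λ = −ln(p)/3.68, and the share of on-drug conceptions ending later is 1 − [1 − exp(−λ(L − g))]/[1 − exp(−12λ)]. For p = 0.7 and L = 12, λ = 0.097 and the share is 60.6%.

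**Early endings.** Suppose a fraction e of pregnancies end at about 10 weeks (2.30 months). Of these, 1 − (12 − 2.30)/12 = 19.2% end after month 12 and 1 − (13 − 2.30)/12 = 10.8% after month 13. For e = 0.5: 0.5 × 72.8 + 0.5 × 19.2 = 46.0%.

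| Scenario | Ends after month 12 | Ends after month 13 |
|---|---|---|
| 38 weeks, even conception | 72.8% | 64.5% |
| 34 weeks | 65.2% | 56.8% |
| 40 weeks | 76.7% | 68.3% |
| 38 weeks, 70% on drug at 16 weeks | 60.6% | 50.8% |
| 38 weeks, 50% on drug at 16 weeks | 48.8% | 38.4% |
| 38 weeks, 20% end early | 62.1% | 53.8% |
| 38 weeks, 50% end early | 46.0% | 37.7% |
| 34 weeks, 50% on drug at 16 weeks | 39.2% | 30.4% |

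The discontinuation rows cover conceptions on drug only. A participant who stops olanzapine can stay in the study (7.10), and a later pregnancy is still reportable.

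**Against the visit schedule.** This part needs no assumption about when conceptions cluster. At 38 weeks, a conception after the 16-week visit reaches term after 16 + 38 = 54 weeks, beyond month 12. A conception after month 6 reaches even 34 weeks only after 26 + 34 = 60 weeks, beyond both month 12 (52 weeks) and month 13 (56.5 weeks). A term pregnancy conceived at month 12 ends at about 12 + 8.74 = 20.7 months.

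**The case against.** The other side has several fair points.

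- A reader might infer that a congenital anomaly could never be detected. The documents do not support that. Conceptions in roughly the first three to four months can reach term within the 12- or 13-month window. After that, 9.2 still has related or unexpected SAEs reported when the chief investigator learns of them, and 9.7 has SUSARs reported however late. These routes govern the reporting of what becomes known, however, and ask nobody to find out.
- A reader might infer that a pregnancy first found at month 12 gets no follow-up of any kind. Pregnancy follow-up under 9.1 does end that day, but "The active monitoring period for (S)AEs will end 13 months after baseline", so about one further month of active monitoring remains. A term birth would still fall outside it.
- That most on-drug pregnancies end too late is not a fact stated in the protocol. It depends on gestation, the timing of conception, discontinuation and early endings, and it fails in some scenarios above.
- The seriousness list is introduced as a regulatory definition, so it is not by itself a promise to collect birth outcomes. Likewise, 7.8 speaks of planned assessments and does not forbid safety reporting.
- Section 2.4 says the study is not meant to establish safety. With 55 patients, pregnancy excluded and contraception required, very few cases are likely.

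These points limit the size of the problem. They do not supply an active route to the outcome of a pregnancy that the protocol requires to be reported.

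**Conclusion.** The point holds as a gap in active ascertainment. Under 9.1, a term pregnancy conceived after about week 14 has no planned collection of its outcome. With even conception and full-term pregnancies, about 73% end after month 12 (65-77% for 34-40 weeks) and about 65% after month 13. At 38 weeks, with half of participants off drug by 16 weeks or half of pregnancies ending early, this falls to about 46-49% after month 12 and 38% after month 13. The percentages rest on the stated assumptions, because the protocol gives neither a pregnancy rate nor conception timing. A substantial share is missed in every scenario examined.

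Sections 9.1 and 7.13.2 also disagree: one follows the pregnant participant to month 12, the other withdraws her. Sites acting on 7.13.2 could stop collecting data sooner still.

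The effect is on the completeness of safety data for a very small expected number of cases. No recruitment, adherence or completion estimate changes.

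**What to change.** Amend 9.1 so that, with the participant's consent, the pregnancy outcome and the newborn's status are recorded whenever they occur, on a short outcome form. Any anomaly should be reported as an SAE. Because 9.1 defines an adverse event as something occurring in a participant, say explicitly that the newborn is covered. State that this is an exception to 7.8 and to the 13-month limit in 9.2.

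Reconcile 9.1 with 7.13.2 in the same amendment, so that withdrawal from the study does not end outcome collection.

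The cost is a few amended sentences, one form, a line in the information and consent documents, and a call or letter to the clinical team for what is probably zero to a few participants. The downside is that a rare outcome may arrive after database lock and need a late report.

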9.2 Recording and reporting of SAEs, SARs AND SUSARs

Reporting Responsibilities

All SAEs will be reported immediately to the Chief Investigator and to the Sponsor (excepting those specified in this protocol as not requiring reporting)

- All SAEs will be reported to the main REC where in the opinion of Chief Investigator (CI) the event was:
 - related that is, it resulted from administration of any of the research procedures, and
 - unexpected that is, the type of event is not listed in the protocol as an expected occurrence, within 15 days of the CI becoming aware of the event.

Death as a result of disease progression and other events that are primary or secondary outcome measures are not considered to be SAEs and should be reported in the normal way, on the appropriate CRF.

The active monitoring period for (S)AEs will end 13 months after baseline which is after down-titration of study medication. Following the active monitoring period, the CI will report any related or unexpected SAEs that he becomes aware of. Where a participant withdraws consent for further processing of data, this does not preclude the reporting of SAEs. The participant information sheet will include a section explaining this to the participant.

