9.6 Reporting urgent safety measures

If any urgent safety measures are taken the CI will immediately and, in any event, no later than 3 days from the date the measures are taken, give written notice to the REC of the measures taken and the circumstances giving rise to those measures.

9.7 The type and duration of the follow-up of participants after adverse reactions.

Any SUSAR will be reported to the REC irrespective of how long after administration of Olanzapine the reaction has occurred until resolved.

	Who	When	How	To Whom
SAE (related or	Chief	Within 15 days of CI becoming	SAE Report form for Non-	Main REC with a copy to
unexpected)	Investigator	aware of the event	CTIMPs, available from NRES	the sponsor and DMEC
			website.	Chair
Urgent Safety	Chief	Immediately	By phone	Main REC
Measures	Investigator			
		Within 3 days	Notice in writing setting out	Main REC with a copy sent
			reasons for the urgent safety	to the sponsor. The MREC
			measures and the plan for future	will acknowledge this
			action.	within 30 days of receipt.
Progress Reports	Chief	Annually (starting 12 months	Annual Progress Report Form	Main REC with a copy to
	Investigator	after the date of favourable	(non-CTIMPs) available from the	the sponsor
		opinion)	NRES website	
Declaration of the	Chief	Within 90 days (conclusion)	End of Study Declaration form	Main REC with a copy to
conclusion or early	Investigator	Within 15 days (early	available from the NRES website	the sponsor
termination of the		termination)		
study		The end of study should be		
		defined in the protocol		

Table of reporting responsibilities

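### Section 9.2 and the reporting table set different triggers for sending an SAE to the REC (related and unexpected, versus related or unexpected), and expectedness has two references

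*Protocol*

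**What the plan says.** Protocol section 9.2 introduces the REC rule with "All SAEs will be reported to the main REC where in the opinion of Chief Investigator (CI) the event was" and then gives two conditions. The first is "related that is, it resulted from administration of any of the research procedures, and" and the second is "unexpected that is, the type of event is not listed in the protocol as an expected occurrence", with a limit of 15 days from the CI becoming aware. The conditions are joined, so both must hold.

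The table of reporting responsibilities, which follows 9.7, has a row that begins "SAE (related or" and continues with the word unexpected on the next line of the cell. The reporter is the CI, the limit is 15 days, and the recipient is the main REC with a copy to "the sponsor and DMEC" Chair. Here either condition is enough.

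Later in 9.2, for the time after active monitoring ends (13 months after baseline), "the CI will report any related or unexpected SAEs that he becomes aware of". That sentence names no recipient and no deadline.

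Expectedness has two references. Section 9.1 defines an unexpected adverse reaction by nature and severity against "The summary of product characteristics (SmPC) for that product (for products with a marketing authorisation"). Section 9.2 asks instead whether "the type of event is not listed in the protocol as an expected occurrence". No list in the protocol is titled a list of expected occurrences. The nearest is in 9.4, which exempts a set of known olanzapine reactions, and routine admissions for standard AN care, from reporting. It sets no limit by seriousness on the exempted reactions.

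**The concern.** The 9.2 bullets and the table govern the same act: the CI telling the main REC about an individual SAE within 15 days. They give different answers for some events, and the protocol does not say which prevails. A simple misprint in the table is not the obvious explanation, because 9.2 itself uses the either-condition wording for the period after monitoring.

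The DMEC Chair is affected as well. The table row is the only place that sends an individual SAE to the Chair; 9.2 does not mention the DMEC. A CI who works from the 9.2 text would not copy the Chair on any SAE. A CI who works from the table would do so for every SAE that is related or unexpected.

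The study gives an off-label drug to participants from age 12, and section 6 says the SmPC does not recommend it below 18 for lack of safety and efficacy data. Which serious events promptly reach independent eyes should not depend on the line that is read.

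**Working it through.** No figure in the protocol is at issue, so the check is a comparison of rules.

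**Inputs**

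| Place | Trigger | Recipient | Deadline |
|---|---|---|---|
| 9.2, bullets | related AND unexpected | main REC | 15 days |
| Table of reporting responsibilities | related OR unexpected | main REC, copy to sponsor and DMEC Chair | 15 days |
| 9.2, after active monitoring | related OR unexpected | none named | none named |
| 9.2, opening line | all SAEs except those exempted | CI and sponsor | immediately |
| 9.7 | SUSAR | REC | none named; applies however late the reaction |

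**Step 1: classify SAEs by the two conditions**

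| Class | 9.2 bullets | Table |
|---|---|---|
| Related, unexpected | REC | REC and DMEC Chair |
| Related, expected | not sent | REC and DMEC Chair |
| Unrelated, unexpected | not sent | REC and DMEC Chair |
| Unrelated, expected | not sent | not sent |

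The 9.2 bullets report 1 class of 4 and the table reports 3 of 4, so 3 − 1 = 2 classes are in dispute. These are logical classes, not event counts. The protocol gives no expected SAE rate, so the number of affected events in 55 patients cannot be derived from it.

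**Step 2: test the two disputed classes against the other rules**

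- *Unrelated, unexpected.* Take a non-routine admission that the CI judges unrelated and whose type the protocol does not list. The 9.4 exemption does not reach it, and it is not a SUSAR because it is not a reaction. The table sends it to the REC and the DMEC Chair; the 9.2 bullets send it to neither. The clash here is clean.
- *Related, expected.* Under 9.2, expected means listed in the protocol. If 9.4 is that list, the same reactions are also declared exempt from reporting. If the exemption covers serious forms, the table row may never apply to them. If it covers only non-serious forms, the table requires a report and the 9.2 bullets do not. The protocol does not settle this, so the class is disputed subject to how 9.4 is read.

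**Step 3: cross the two references for expectedness, for a related SAE**

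| In SmPC | In protocol list | Label under 9.1 | Label under 9.2 |
|---|---|---|---|
| yes | yes | expected | expected |
| yes | no | expected | unexpected |
| no | yes | unexpected | expected |
| no | no | unexpected | unexpected |

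The labels disagree in two of the four rows. With each definition used only where it is written, neither disagreement by itself loses a REC report. Row 2 is reported under the 9.2 bullets. Row 3 is a SUSAR and goes to the REC under 9.7, subject again to 9.4. The difficulty is that the table uses the word unexpected without saying which definition it takes, so two careful readers can classify one event differently.

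A smaller ambiguity has the same effect: related in 9.2 refers to research procedures, whereas an adverse reaction in 9.1 refers to the medicinal product.

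**The case against.** The strongest reply is that this is a wording clash with little practical reach. Much of that reply stands:

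- All non-exempt SAEs go at once to the CI and sponsor, whichever trigger applies.
- SUSARs go to the REC in any case.
- The DMEC reviews accruing data under section vi.
- The withdrawal and whole-trial stopping criteria in 7.10 do not depend on this trigger.
- No estimate or analysis changes.

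A reader might also infer more than the documents support, in four ways:

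- *That every serious form of a known olanzapine reaction escapes the REC under 9.2.* It does not. A related reaction that is in the SmPC but not listed in the protocol is unexpected under 9.2 and is reported under both rules. A form whose nature or severity is inconsistent with the SmPC is a SUSAR.
- *That the reporting net is deliberately wider after monitoring than during it.* The post-monitoring sentence names no recipient or deadline, so it cannot be compared like for like with the REC rule.
- *That independent oversight as a whole turns on the sentence chosen.* Only the prompt individual notice does.
- *That the secondary objective on the quality of adverse event reporting is compromised.* Section 3.5 ties that to the UKU-SERS, and 10.3.3 summarises AEs and SAEs; routing to the REC changes neither.

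Nor does the protocol show which trigger was intended. Two places use the either-condition form, but one of them names no recipient, and a slip in the table cannot be excluded.

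None of this removes the contradiction between two operative rules with the same reporter, recipient and clock.

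**Conclusion.** The protocol contradicts itself on when the CI must send an individual SAE to the main REC, and the only stated individual copy to the DMEC Chair hangs on one side of that contradiction. Two of the four related/unexpected classes are affected. The unrelated, unlisted SAE is affected outright. The related SAE of a listed type is affected only if the 9.4 exemption does not extend to serious events. The two references for expectedness are a real inconsistency, but as written they add uncertainty of classification rather than a demonstrated loss of reports.

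The consequence is limited to prompt individual notification of the REC and DMEC Chair. The conclusion rests on the protocol text alone and assumes that no other safety document, not shown, sets an order of precedence. It does not say which trigger is right.

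**What to change.** Amend section 9 as follows:

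1. Reconcile the 9.2 bullets and the table to one stated trigger. If the REC and the DMEC Chair are meant to have different thresholds, give each its own table row.
2. State the copy to the DMEC Chair in the 9.2 text as well as in the table.
3. Name one reference for expectedness and use it in 9.1, in 9.2 and in the table. If it is a protocol list, title it as such.
4. State whether the 9.4 exemption applies to events that meet the serious criteria in 9.1.
5. Give the post-monitoring sentence in 9.2 the same trigger, with a recipient and a deadline.

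The cost is a wording amendment and, depending on the trigger chosen, possibly a few more SAE copies in a 55-patient study.
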